9.4.2.2 Efficacy Analyses

Endpoint	Statistical Analysis Methods
Primary	Not applicable.
Secondary	Listings of secondary efficacy endpoints will be produced for all subjects. The proportion of subjects with an OR (per modified RECIST 1.1) and 95% CI will be tabulated by planned dose level. For all subjects treated at the MTD and/or RP2D, Kaplan-Meier methods will be used to estimate the time to event curve, median time to event and percentiles with 95% CI for 1) duration of response; 2) time to progression; 3) progression-free survival; 4) time to subsequent therapy; 5) overall survival; 6) time to response. For all subjects treated at the MTD and/or RP2D, Kaplan-Meier methods will be used to estimate landmarks for time to event endpoints (eg, 1-year PFS) with 95% CI).

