5.1.2 Secondary Endpoints Definitions

Objective Response (OR) per RECIST 1.1:

Objective Response is defined as a best overall response ([Appendix C](#)) of either Complete Response (CR) or Partial Response (PR) per RECIST 1.1. Radiographic response (Complete Response, Partial Response) requires confirmation by a repeat, **evaluable** scan at least 28 days after the first documentation of response.

Subjects who do not experience a PR/CR or do not have any follow-up tumor assessments will be regarded as non-responders.

Overall Survival (OS):

Overall survival is defined as the time from the date of Study Day 1 until death due to any cause:

$$\text{OS time (Days)} = \text{date of death} - \text{Study Day 1} + 1.$$

Any subject not known to have died at the time of analysis will be censored based on the last recorded date on which the subject was alive.

Duration of Response (DOR):

The duration of response is defined as time from first evidence of CR or PR to disease progression or death due to any cause, whichever occurs first. DOR will be calculated only for subjects who achieve a best overall response of PR or CR.

$$\text{DOR (months)} = (\text{PD / death date} - \text{response start date} + 1) \times 12 / 365.25$$

The time of the initial response will be defined as the earliest of the dates contributing towards the first visit response of PR or CR.

- For confirmed responders whose PR or CR are confirmed in two **evaluable** assessments, the first PR/CR assessment among the two **evaluable** assessments will be used to calculate DOR.
- For unconfirmed responders awaiting follow-up confirmation scans, the PR or CR assessment that is awaiting confirmation scan will be used to calculate DOR.

Censoring rules for Duration of Response (DOR):

- Data for responders who are alive and without disease progression or new anti-cancer therapy are censored at the time of last **evaluable** tumor assessment **by CT/MRI scan**.
- Data for responders who are alive and without disease progression but who start new anti-cancer therapy are censored at the time of last **evaluable** tumor assessment **by CT/MRI scan** before the start of new anti-cancer therapy.
- Data for responders who die or have disease progression after two or more missed evaluable tumor assessments are censored at the time of last evaluable tumor assessments **by CT/MRI scan** before the two or more missed evaluable tumor assessments.

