Details about the censoring rules are included in [Appendix E](#).

Radiographic Progression:

Disease progression per RECIST 1.1 occurs.

Radiographic Progression-free Survival (radiographic PFS):

Radiographic PFS is defined as the interval from Study Day 1 to the earlier of a radiographic progression or death from any cause; otherwise **PFS is censored based on criteria in [Appendix E](#)**.

Clinical Progression:

Clinical disease progression is based on clinical symptoms and are not associated with radiologic progression.

This is recorded by the field ‘disease progression is equal to clinical progression’ on the EOIP eCRF page.

Details about the censoring rules are included in [Appendix E](#).

Clinical Progression-free Survival (clinical PFS):

Clinical PFS is the time from Study Day 1 to clinical disease progression or death from any cause.

Details about the censoring rules are included in [Appendix E](#).

Time to Response (TTR):

TTR is defined as the time from the date of Study Day 1 to the date of the first documented CR or PR that is subsequently confirmed per RECIST1.1. For a subject who did not respond, time to response will be censored at the latest evaluable radiological assessment date. If a subject has no tumor evaluation in the study, time to response will be censored at the date of Study Day 1.

The time of the initial response will be defined as the earliest of the dates contributing towards the first visit response of PR or CR.

- For confirmed responders whose PR or CR are confirmed in two **evaluable** assessments, the first PR/CR assessment among the two **evaluable** assessments will be used to calculate TTR.
- For unconfirmed responders awaiting follow-up confirmation scans, the PR or CR assessment that is awaiting confirmation scan will be used to calculate TTR.

Time to Radiographic Progression:

Time to radiographic progression is defined as the interval from Study Day 1 to radiographic progression; otherwise, time to radiographic progression is censored based on the criteria in [Appendix E](#).

Time to Clinical Progression:

Time to clinical progression is defined as the interval from Study Day 1 to clinical progression; otherwise, time to clinical progression is based on the criteria in [Appendix E](#).

Subsequent Therapy:

Subsequent therapy is defined as subjects receiving anti-cancer therapies intended to treat NSCLC or any other anti-cancer therapies prior to end of study.

Time to Subsequent Therapy:

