6.2 RECIST 1.1 Evaluable Analysis Set

RECIST 1.1 Evaluable Analysis Set is defined as all subjects that are enrolled, receive at least 1 dose of investigational product (AMG 160) and have measurable baseline disease per RECIST 1.1 per protocol and have the opportunity to be followed for at least 9 weeks starting from Study Day 1. Subjects who stopped disease assessment prior to 9 weeks will be included in this analysis set if the data cutoff is at least 9 weeks after their Study Day 1.

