9.5.2 Analyses of Secondary Efficacy Endpoint(s)

[figure not shown]
For the secondary efficacy endpoints mentioned below, we will consider the endpoints to be derived and presented separately for the Central review and the Investigator's review except for the overall survival, clinical progression-free survival, time to clinical progression and time to subsequent therapy.

Table 9-1. Secondary Efficacy Endpoint Summary Table

Endpoint	Statistical Analysis	Analysis Set
Objective response per modified Response Evaluation Criteria in	The proportion of subjects with an objective response per modified RECIST 1.1 along with the corresponding	RECIST 1.1 Evaluable Analysis Set

Endpoint	Statistical Analysis	Analysis Set
Solid Tumors (RECIST) 1.1	
exact 95% CI will be calculated using the Clopper-Pearson method (Clopper and Pearson, 1934)
 
Waterfall plots for the maximum percent decrease from baseline in sums of longest diameters will also be provided.
	Applicable for all subjects with measurable baseline disease and at least one post-baseline evaluable tumor response assessment
Overall Survival (OS)	OS will be estimated and the median and other percentiles, as appropriate, will be presented using the Kaplan-Meier curve and 95% CI using Greenwood's formula to estimate the standard error of the landmark estimates, see (Kalbfleisch and Prentice, 1980).	Safety Analysis Set
Radiographic Progression Free Survival (PFS) Clinical Progression Free Survival (clinical PFS)	The median and other percentiles as appropriate, will be presented using the Kaplan-Meier curve and 95% CI using the Brookmeyer and Crowley (Brookmeyer and Crowley, 1982) method.	Safety Analysis Set
Time to Response (TTR)	The median and other percentiles as appropriate, will be presented using the Kaplan-Meier curve and 95% CI using the Brookmeyer and Crowley (Brookmeyer and Crowley, 1982) method.	RECIST 1.1 Evaluable Analysis Set
Time to Progression (TTP) Radiographic Time to Progression (TTP) Clinical	The median and other percentiles as appropriate, will be presented using the Kaplan-Meier curve and 95% CI using the Brookmeyer and Crowley (Brookmeyer and Crowley, 1982) method.	Safety Analysis Set
Duration of Response (DOR)	The median and other percentiles as appropriate, will be presented using the Kaplan-Meier curve and 95% CI using the Brookmeyer and	RECIST 1.1 Evaluable Analysis Set

Endpoint	Statistical Analysis	Analysis Set
	Crowley (Brookmeyer and Crowley, 1982) method.	

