Timepoint Response by Central Review:

Timepoint response by Central Review is the Overall response at each tumor assessment as assessed by Central radiographic reader(s). This data is usually non-CTDB dataset transferred from Central Review vendor.

Confirmed BOR by Central Review:

Confirmed BOR by Central Review will be derived from the Timepoint Response by Central Review in the same way as Confirmed BOR by Investigator.

Interim BOR by Central Review:

Interim BOR by Central Review will be derived from Timepoint response by Central Review in the same way as Interim BOR by Investigator.

Best Overall Response (BOR):

The best overall response is the best observed disease response recorded from the start of the study treatment until disease progression/recurrence, the start of new anticancer therapy or the end of study. Confirmed BOR by Investigator, Interim BOR by Investigator, Confirmed BOR by Central Review, Interim BOR by Central Review have been separately defined above.

The followings steps would be followed to derive ORR as per RECIST 1.1.

Table 14.1. BOR per RECIST 1.1 where confirmation of CR/PR is required

[figure not shown]
Criterion	Time point T1 Response	T1 ≥ 49 days after Baseline?	Time point T2 Response	T2 ≥ 49 days after Baseline?	T2 ≥ 28 days after T1?	Confirmation	
C1	CR	Yes	CR	-	Yes	CR	
C2			CR	-	No	SD	
C3			PR, SD	-	-	Query data*	
C4			PD	-	-	SD	
C5			NE, No further evaluations			SD	
C6		No		CR	-	Yes	CR
C7				CR	Yes	No	SD
C8				PR, SD	-	-	Query data*
C9				PD	-	-	PD
C10				NE, No further evaluations			NE
C11	PR	Yes	CR, PR	-	Yes	PR	
C12			CR, PR	-	No	SD	
C13			SD	-	-	SD	
C14			PD	-	-	SD	
C15			NE, No further evaluations			SD	
C16		No		CR, PR	-	Yes	PR
C17				CR, PR	Yes	No	SD
C18				SD	Yes	-	SD
C19				PD	-	-	PD
C20				NE, No further evaluations			NE
C21	SD	Yes	CR, PR, SD, PD, NE, no more evaluation			SD	
C22			No	CR, PR, SD	Yes	-	SD
C23		CR, PR, SD		No	-	NE	
C24		PD		-	-	PD	
C25		NE, No further evaluations			NE		
C26	PD		-		PD		
C27	NE	-	NE, No further evaluations			NE	
C28		-	CR, PR, SD	Yes	-	SD	
C29		-	CR, PR, SD	No	-	NE	
C30		-	PD	-	-	PD	

CR = complete response, PR = partial response, SD = stable disease, PD = progressive disease, and NE = not evaluable.

*If a CR is truly met at first time point, then any disease seen at a subsequent time point, even disease meeting PR criteria relative to baseline, makes the disease PD at that point (since disease must have reappeared after CR). Best response would depend on

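### Kaplan-Meier for time to response censors subjects who can no longer respond, so the curve overstates response and its median is usually unreached; ORR and the decision rules are unaffected

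*SAP*

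**What the plan says.** SAP 5.1.2 measures TTR from Study Day 1 to the first CR or PR that is later confirmed. For everyone else the rule is "For a subject who did not respond, time to response will be censored at the latest evaluable radiological assessment date". It adds: "If a subject has no tumor evaluation in the study, time to response will be censored at the date of Study Day 1". Non-responders who progressed, died or began new treatment get no separate rule, and Appendix E has no TTR table.

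Table 9-1 in SAP 9.5.2 gives the method for TTR: "The median and other percentiles as appropriate, will be presented using the Kaplan-Meier curve and 95% CI using the Brookmeyer and Crowley". The population is the RECIST 1.1 Evaluable Analysis Set, not the responders. SAP 6.2 says of that set: "Subjects who stopped disease assessment prior to 9 weeks will be included in this analysis set", provided the data cutoff is late enough. Protocol 9.4.2.2 plans the same type of analysis and lists time to response sixth among the endpoints: "For all subjects treated at the MTD and/or RP2D, Kaplan-Meier methods will be used to estimate the time to event curve".

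Three other SAP provisions matter here:

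- **Appendix C limits when a response can count.** "The best overall response is the best observed disease response recorded from the start of the study treatment until disease progression/recurrence", with new anticancer therapy and end of study as the other stopping points. For this purpose progression needs no confirmation.
- **For ORR, the same subjects stay in the denominator.** "Subjects who do not experience a PR/CR or do not have any follow-up tumor assessments will be regarded as non-responders".
- **Duration of response is limited to responders.** TTR has no such restriction.

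**The concern.** Kaplan-Meier assumes that a censored subject has the same future chance of the event as those still under observation. That is reasonable for a subject who is progression-free and awaiting the next scan. It is false for one who has progressed, died or switched treatment: under the SAP's own definition, that subject's chance of a countable response is zero. Removing such subjects from the risk set passes their probability to those who remain.

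Two outputs suffer. The curve rises above the proportion who actually responded, and it will appear in the same report as the ORR. The planned median has no natural meaning when far fewer than half of subjects respond: either it is not reached, or it appears because the risk set has been emptied of progressors.

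**Working it through.** **Planning figures.** The documents give no TTR figure, so I start from their response-rate figure. For 8 responders of 40, the Clopper-Pearson interval is 9.05% to 35.65%, which reproduces the 9% to 36% in SAP 3.2. The futility rule in SAP 7.1 refers to an ORR of 15%. CT/MRI is every 8 weeks with a 7-day window either side (protocol Table 1-6).

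**Direction.** Let d_i be the responses and r_i the number at risk at the i-th response time. Kaplan-Meier gives 1 − Π(1 − d_i/r_i). Since r_i can never exceed n minus the earlier responses, this is at least (total responses)/n. It is strictly larger whenever a non-responder is censored before a later response. The direction therefore needs no assumption about timing.

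**Hand example (illustrative counts).** Take 40 subjects, 8 responding: 5, 2 and 1 at weeks 8, 16 and 24. Of the 32 non-responders, 4 progress or die without a scan; 14, 7 and 4 progress at those three scans; 3 stay stable to week 32.

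| Week | At risk, SAP rule | Responses | 1−KM | Cumulative incidence, progression and death competing |
|---|---|---|---|---|
| 8 | 40 − 4 = 36 | 5 | 1 − 31/36 = 13.9% | 5/40 = 12.5% |
| 16 | 36 − 5 − 14 = 17 | 2 | 1 − (31/36)(15/17) = 24.0% | 7/40 = 17.5% |
| 24 | 17 − 2 − 7 = 8 | 1 | 1 − (31/36)(15/17)(7/8) = 33.5% | 8/40 = 20.0% |

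The Kaplan-Meier median is not reached. The median among the 8 responders is week 8. Cumulative incidence ends at the ORR; 1−KM ends 13.5 points above it.

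**Simulation, n = 40.** The following are assumptions, not in the documents: median time to progression or death in non-responders of 8 to 20 weeks; up to 10% of non-responders never scanned; responses split over the first three scans from 80/15/5 to 40/30/30 percent.

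| Scan timing | True ORR | Mean 1−KM | Median not reached |
|---|---|---|---|
| On the nominal day | 15% | about 16% to 32% | about 78% to 100% (both ORRs together) |
| On the nominal day | 20% | about 21% to 40% | as above |
| Spread over the 7-day window, 10% never scanned | 15% | 20% to 40% | 77% to 100% |
| Spread over the 7-day window, 10% never scanned | 20% | 26% to 49% | 53% to 99.7% |

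Spreading the scans raises the bias because some progressors leave the risk set before responses recorded later in the same visit window.

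**Check with expected counts, ORR 20%, scans on the nominal day.**

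- *Upper end* (progression median 8 weeks, 40/30/30, 10% unscanned). Responses are 3.2, 2.4 and 2.4. Of 28.8 scanned non-responders, half of those remaining progress in each interval, so 14.4 leave at week 8 and 7.2 at week 16. Risk sets are 36.8, 19.2 and 9.6. Then 1 − (33.6/36.8)(16.8/19.2)(7.2/9.6) = 40.1%.
- *Near the lower end* (median 20 weeks, 80/15/5, all scanned). The fraction still progression-free after each interval is 2^(−8/20) = 0.758. Risk sets are 40, 25.85 and 18.78, with 6.4, 1.2 and 0.4 responses. Then 1 − (33.6/40)(24.65/25.85)(18.38/18.78) = 21.6%.

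**What a reached median would mean.** At a true ORR of 20% with n = 40, the binomial probability that half or more respond is 0.00002. A cumulative-incidence curve would practically never reach 50%.

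**The case against.** The strongest reply is that little depends on this endpoint. Response is reported as ORR with an exact interval and non-responders in the denominator. The futility and expansion rules count responders, no hypothesis is tested, and TTR is descriptive. All of that stands, and it limits the importance of the point.

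A reader might infer that the plan will tabulate an inflated response probability that contradicts the ORR. The documents do not support that. SAP 9.1 confines landmark estimates to overall survival, and Table 9-1 plans percentiles for TTR. The excess would be seen only by reading the plotted curve.

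A reader might also infer that the median will almost never be reached. That is too strong: with fast progression and later responses it was unreached in as few as 53% of trials at an ORR of 20%. At an ORR of 30% the range was 16% to 91%.

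The size of the bias rests on progression and response timing that the documents do not give. With early responses and slow progression it is only a few points. The direction does not depend on these assumptions.

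Two further defences fail. Treatment may continue past a first, unconfirmed progression, but Appendix C does not require confirmation of progression for best response, so a later response would not count. The condition of more than 10 events in SAP 7.1 applies only to the interim analysis. Table 9-1's wording may let the team omit an unreached median, but it does not correct the curve.

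**Conclusion.** The point holds as an error confined to one secondary endpoint. Censoring subjects who have progressed, died or started new therapy is informative under the SAP's own response definition, and nothing elsewhere in either document corrects it. The 1−KM curve cannot fall below the observed response proportion, and it exceeded the true ORR on average in every scenario run.

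The illustrative size is about 16% to 32% against a true 15%, and 21% to 40% against a true 20%, with somewhat higher values once the visit window is modelled. At those response rates the median is usually unreached, and one that does appear is largely an artefact of emptying the risk set. The sizes depend on the assumed timing; the direction does not. It is worth correcting before database lock, but it does not threaten the trial's conclusions on response.

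**What to change.** In SAP 5.1.2 and Table 9-1, restrict TTR to confirmed responders and report the number, median and range, in line with the restriction already placed on duration of response. This removes the need for a censoring rule. The bullet in SAP 5.1.2 that times responders still awaiting confirmation should be marked as interim-only, since TTR is defined by confirmed response.

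If a curve is wanted, plot the cumulative incidence of response in the evaluable set (Aalen-Johansen), with progression, death and new anticancer therapy as competing events. Censor only subjects still at risk of a response, and add the matching TTR table to Appendix E.

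Protocol 9.4.2.2 also prescribes Kaplan-Meier for time to response in all subjects at the MTD and/or RP2D. Record the departure in SAP Section 10, and align the protocol text if it is next amended.

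The cost is a few lines of SAP text and a simpler table. No new data, visits or subjects are needed.

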5.2 Study Time Points

Enrollment Date:

A subject is considered as enrolled when the investigator decides that the subject has met all eligibility criteria. The investigator should document this decision and date in the subject's medical record and in the enrollment case report form.

Study Day 1:

Study Day 1 is defined as the date of the first dose of the AMG 160 administered to the subject.

End of Study for Individual Subject:

End of study for individual subject is defined as the date of the subject last completed a protocol-specified procedure. The date will be recorded on the End of Study eCRF page.

End of Treatment:

End of treatment is defined as the date the decision was made to end investigational product (AMG 160) as recorded on the End of Investigational Page eCRF page.

Safety follow-up Visit:

Safety follow-up visit is defined as upon permanent discontinuation from the study treatment for any reason, a safety follow-up visit will be performed approximately 30 (+3) days after the end of the last dose of AMG 160, or prior to initiation of other therapy, whichever occurs first.

Long-term follow-up Visit:

Long-term follow-up visit will be conducted every 6 months up to 3 years from the first dose of AMG 160 for all subjects who have not withdrawn consent by clinic visit, telephone or chart review to assess for survival and/or the commencement of subsequent cancer therapy.

5.3 Demographics and Baseline Related Definitions

Age at enrollment:

Subject age at enrollment will be collected in years reported in the clinical database.

Baseline:

The baseline is defined as the last non-missing value on or prior to the pre-dose assessments of AMG 160 on cycle 1 day 1.

Baseline for Triplicate ECG:

Baseline for ECG is defined as mean of the 3 triplicate ECG results. If fewer than 3 triplicate ECG results are available, the mean of available triplicate should be calculated. For all post-baseline ECG, the mean of one triplicate ECG results at the same assessment will be calculated and used in the analysis.

When an ECG is missing within a triplicate, all available data will be averaged for that timepoint.

Triplicate ECGs (to be only performed if the dose being evaluated is higher than the MTD established in subjects with mCRPC [Study 20180101])."

Change from Baseline:

Change from Baseline is the arithmetic difference between post-dose assessments and Baseline.

Change from Baseline = (Post-baseline Value – Baseline Value).

Investigational Product:

The term investigational product is used in reference of AMG 160 (acapatamab).

Percent Change from Baseline:

Percent change from baseline is the arithmetic difference between post-baseline and baseline divided by baseline values times 100.

Change (Percent) from Baseline = [(Post-baseline Value – Baseline Value)/Baseline Value] x 100.

6. Analysis Sets

The following sub-sections describe the analysis sets to be used.

6.1 Safety Analysis Set

The analysis of all endpoints, unless noted otherwise, will be conducted on the Safety Analysis Set defined as all subjects that are enrolled and receive at least 1 dose of AMG 160.

6.2 RECIST 1.1 Evaluable Analysis Set

RECIST 1.1 Evaluable Analysis Set is defined as all subjects that are enrolled, receive at least 1 dose of investigational product (AMG 160) and have measurable baseline disease per RECIST 1.1 per protocol and have the opportunity to be followed for at least 9 weeks starting from Study Day 1. Subjects who stopped disease assessment prior to 9 weeks will be included in this analysis set if the data cutoff is at least 9 weeks after their Study Day 1.

